7.4 Recruitment Materials

We may use flyers, web postings, social media ads, emails and a video posted on the REDCap study page to inform potential participants about the study. Materials will include a study email address for individuals to use if they have questions about the study. Recruitment will occur on a continuous basis throughout the 3-year study.

7.5 Compensation

- Pre-Intervention Assessment = \$0
- Week 1 Assessment = \$10
- Week 2 Assessment = \$10
- Week 3 Assessment = \$10
- Post-Intervention Assessment = \$40
- 3-Month Follow-Up Assessment = \$45
- Stool sample collection = \$60 (\$30 for pre-intervention and \$30 for follow-up)
- Dried blood spot collection = \$40 (\$20 for pre-intervention and \$20 for follow-up)
- Bonus for Completing Above 6 Assessments = \$50
- Total: up to \$265

Payment will be via check and provided at the end of participation in the study (after the 3-month follow-up assessment) or via a pre-loaded and reloadable debit card issued by US Bank. The debit card will be mailed to participants after they finish the week 1 assessment. After each assessment is completed, the next payment amount will be loaded onto the debit card. If participants choose to withdraw or are taken off the study for any reason, they will receive payment for the assessments they have completed. Individuals excluded based on the interview will be paid \$15 for their time spent completing the pre-intervention assessment and interview.

Individuals who have a visa will be informed in the webscreen and the consent form that due to UW-Madison limitations on payments, we can only provide monetary compensation to individuals who are US citizens or residents (green card holders). The webscreen asks individuals if they are still interested in participating after being informed about this restriction of payment.

Pilot participants will be paid up to \$75: \$40 for the Pre-Intervention Assessment, \$10 for the Week 1 assessment, \$15 for the stool sample, and \$10 for the dried blood spot.

Healthy control participants will not be paid for the pre-intervention assessment, but will be paid \$30 for the stool sample collection, \$20 for the dried blood spot collection, and a \$35 bonus for completing all study measures.

8.0 Consent Process

PROTOCOL TITLE: Behavior, Biology, and Well-Being (BeWell) Study

8.1

The consent process is a waiver of written documentation of consent. A link to the consent script will be emailed via REDCap to eligible potential participants after they complete their screening surveys. Individuals are informed in the instructions for the consent script as well as within the consent script to reach out to study staff if they have any questions before proceeding. Clicking a box will indicate one's interest in taking part in the study.

9.0 Process to Document Consent in Writing

9.1

N/A

9.2

We are waiving written documentation of consent. A consent script will be sent to eligible potential participants via REDCap after eligibility is confirmed. Individuals will check a box if they agree to participate in the study. After clicking the box, participants are informed that the next steps are to complete the initial surveys and games, a dried blood spot and stool sample kit will be mailed to them, and they will be scheduled for the interview.

This study involves minimal risk and involves no procedures for which written consent is normally required outside of the research context. The waiver will not adversely affect the rights and welfare of the participants. It will be made clear that they can withdraw at any time.

10.0 Setting

10.1 Location

Research procedures will be performed remotely.

11.0 Study Intervention

11.1

The study intervention will be the Healthy Minds Program (HMP), a 4-week mobile health meditation training augmented with depression-specific content. The HMP was developed by our affiliated non-profit organization, Healthy Minds Innovations, Inc (HMI). The HMP is designed to promote and protect psychological well-being through sustainable skills training, with instruction administered through a curriculum of high-quality guided practices. The HMP is based on research on eudaimonic well-being (e.g., environmental mastery, purpose) and brain-based skills that underlie these qualities (e.g., regulation of attention, mental flexibility). The HMP has >100 guided audio practices that address 4 constituents of well-being: awareness, connection, insight, and purpose. The intervention and active control groups will download and use a study specific version of the HMP immediately after randomization. The intervention group will have access to and instructed to listen to both the lessons and meditations (guided practices). The active control group

PROTOCOL TITLE: Behavior, Biology, and Well-Being (BeWell) Study

will have access to and instructed to listen to the lessons only (meditation practices are not included). The intervention and active control groups will use the HMP for four weeks. The active control group and the usual care group will be given the opportunity to download and use the full HMP after they finish their 3-month follow-up assessment.

The following usage data is recorded: date, time, duration, device type, lesson or practice, week, foundation (awareness, connection, insight, or purpose), and name of lesson or practice.

Participants listen to lessons and/or practices and occasionally answer pre and post questions using their smartphones.

This study requested a non-significant risk (NSR) determination for the use of the HMP. Use of the HMP may mitigate symptoms of depression, anxiety and/or stress but has not shown to pose a risk to health or safety. Below is a copy of the NSR letter.

Request for a Non-Significant Risk Determination from the IRB for an Investigational Device

UW-Madison Health Sciences IRB:

Please accept this letter as a request for non-significant risk (NSR) determination for the investigational device evaluation described in the IRB submission titled “BeWell Study”.

The FDA defines significant risk devices as follows (21 C.F.R. § 812.3(m)):

- ““(1) Is intended as an implant and presents a potential for serious risk to the health, safety, or welfare of a subject;
- (2) Is purported or represented to be for a use in supporting or sustaining human life and presents a potential for serious risk to the health, safety, or welfare of a subject;
- (3) Is for a use of substantial importance in diagnosing, curing, mitigating, or treating disease, or otherwise preventing impairment of human health and presents a potential for serious risk to the health, safety, or welfare of a subject; or
- (4) Otherwise presents a potential for serious risk to the health, safety, or welfare of a subject””

The Healthy Minds Program (HMP) in this study is a smartphone app that includes both didactic content and guided meditation practices. The device will be used to aid development of well-being by training skills that are based on scientific studies (the didactic content). It also includes guided meditation practices found in widely available evidence-based treatments such as mindfulness-based stress reduction, mindfulness-based cognitive therapy, cognitive behavioral therapy, acceptance and commitment therapy, and other widely used smartphone meditation apps such as Headspace and Calm.

The use of the device in this study does not meet the definition of a significant risk device as it is not an implant, is not used to sustain human life and poses no serious risk to health, safety or

PROTOCOL TITLE: Behavior, Biology, and Well-Being (BeWell) Study

welfare of a subject. The device may mitigate symptoms of depression, anxiety and stress, but has not shown to pose a serious risk to health, safety, or welfare.

Summary of prior uses: HMP has been tested by our group in two randomized controlled trials (ns = 343, 662; Goldberg et al., 2020; Hirshberg et al., 2021). In both trials, HMP was shown to produce larger reductions in psychological distress (composite of depression, anxiety, and stress) relative to a waitlist control condition. Participants in both studies were drawn from the general population, although ~75% in each sample reported elevated depression and/or anxiety symptoms at baseline. Effects were similar when restricted to those in the clinical range at baseline. No serious adverse effects were reported in either study. In support of HMP's safety, HMP was shown to produce lower rates of clinically significant increases in symptoms relative to a waitlist condition.

References:

12.0 Study Timelines

12.1

This will be a 3-year project with participants randomized into 3 groups: HMP intervention group, active control group, and usual care group (see "Randomization", section 13.1.4). Participants will be involved with the study for approximately 4 months. Recruitment will start upon UW Institutional Review Board (IRB) approval and continue until study goals are reached. We estimate that we will complete primary analyses within 3 years of the end of data collection.

In order to ensure that the procedures outlined below are implemented in a feasible and functional way for the intended study participants a pilot of up to 15 participants will precede initiation of the

PROTOCOL TITLE: Behavior, Biology, and Well-Being (BeWell) Study

full study. Pilot participants will be asked to complete all aspects of the study up to and including the week 1 assessments.

A sample of healthy control participants will complete baseline measures only.

13.0 Procedures Involved

13.1 Study Design

After potential participants are informed of their eligibility, they will be invited to complete the following steps:

1. Consent Process. Individuals will read a consent script in REDCap and are given the opportunity to reach out to study staff if they have any questions or concerns about study procedures before clicking on the box indicating interest in participating in the study.
2. Pre-Intervention Assessment (Timepoint 1). A REDCap link for these surveys and games (behavioral task and video task) will be sent after consent is completed. It will take approximately 60-90 minutes to complete these measures. Potential participants will be given two weeks to complete this assessment. In order to increase study retention, only those who complete this assessment will be invited to subsequent parts of the study. A microbiome and blood spot collection kit will be mailed to participants to be completed before randomization occurs. The kit needs to be returned within one month of completing the surveys and games to continue with the randomization step.
3. Interview. The participant will undergo an interview conducted by research staff who are trained in interviewing techniques and supervised by qualified study personnel with mental health expertise. The interview will consist of the depression and related modules of the Structured Clinical Interview for DSM-5 Research Version (SCID-5-RV). The interview will be done via phone or video and will take approximately 60 minutes to complete. Participants may be sent an email to confirm their current phone number, interview time, and/or other details to assist with interview scheduling.
4. Randomization. Participants will be assigned to one of three groups: approximately two-fifths to the HMP intervention group, approximately two-fifths to the active control group, and approximately one-fifth to the usual care group. Randomization will be done in REDCap (either immediately after the interview or within a few days if consultation with a study PI or Co-I is needed; the microbiome and blood spot kit need to be returned before randomization). A REDCap alert will inform participants of group status immediately after randomization along with instructions for downloading HMP for those in the intervention and active control groups.
5. Weeks 1 to 3 Assessments (Timepoints 2, 3, 4). Participants will complete a small subset of the surveys in REDCap as well as the video task at the end of weeks 1, 2, and 3. It will take

PROTOCOL TITLE: Behavior, Biology, and Well-Being (BeWell) Study

approximately 30 minutes to complete these measures. Participants will be given one week to complete each weekly assessment.

6. Week 4/Post-Intervention Assessment (Timepoint 5). Participants will complete the same surveys and games (behavioral task and video task) in REDCap as was done for the pre-intervention assessment; the invite for these measures will be sent at the end of week 4. It will take approximately 60-90 minutes to complete these measures. Participants will be given 2 weeks to complete this assessment. Participants in the intervention or active control groups will have the option to continue using the HMP after this timepoint. We will continue to monitor app data throughout the study to learn more about its long-term impact on well-being.
7. 3-Month Follow-Up Assessment (Timepoint 6). Participants will complete the same surveys and games (behavioral task and video task) in REDCap as was done for the pre-intervention and post-intervention assessments; the invite for these measures will be sent 90 days after the date of the post-intervention invite. It will take approximately 60-90 minutes to complete these measures. Participants will be given 2 weeks to complete this assessment. Another microbiome kit and blood spot collection kit will be mailed to participants to collect samples; they will have 1 month to collect.

Healthy control participants will complete only #1 to #3.

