The data elements collected will be questionnaires, a structured interview, behavioral tasks, and biospecimens. All study materials will be uploaded to the ARROW application. Data will not be collected from any of the following sources:

- UW Health medical or billing records via ICTR's Clinical Research Data Service (CRDS)
- UW Health HealthLink Records (study team will directly access)
- Data from departmental QA or QI database
- Data from UW Health Enterprise Data Warehouse (EDW)
- Data from PACS (Picture Archiving and Communication System)
- Data from Center for Medicare/Medicaid Services
- Data from publicly available datasets (e.g., U.S. census data)
- Data from outside institutions or organizations
- Other

13.5

There are no current plans for long-term follow-up besides the 3-month follow-up that is part of the study procedures listed above. For those in the HMP intervention or active control groups, any data collected through the HMP app (e.g., usage data) will continue to be collected until the 3-month follow-up assessment. Additional follow-up assessments may be planned by study personnel and/or collaborators. The consent form will include language pertaining to permission for future contact.

13.6

N/A

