21.0 Potential Benefits to Participants

21.1

Participants may benefit from using the HMP, which is designed to introduce meditation practice as a way of reducing stress and developing greater balance, ease, and fuller participation in life. This meditation training teaches well-being skills which can be used in everyday life to cope with the challenges of stress, pain, illness, and everyday demands. Usual care and active control participants can use the full version of HMP after completion of the study at no cost.

21.2

There are no direct benefits for participants.

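### The offer of the full HMP to controls does not wait for the 3-month stool and blood-spot samples, so some controls could use the program before their only post-randomization biological sample

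*Combined protocol and SAP*

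**What the plan says.** **Release to controls.** Section 11.1 says that the active control and usual care groups "will be given the opportunity to download and use the full HMP after they finish their 3-month follow-up assessment". Section 21.1 words the condition differently: "Usual care and active control participants can use the full version of HMP after completion of the study at no cost".

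**Follow-up windows.** In section 13.1, step 7, "the invite for these measures will be sent 90 days after the date of the post-intervention invite". The measures meant are the surveys and games, and for these "Participants will be given 2 weeks to complete this assessment". The kits follow in a separate sentence: "Another microbiome kit and blood spot collection kit will be mailed to participants to collect samples; they will have 1 month to collect". The plan does not say when the kit is mailed or when its month begins.

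**Assessments and samples.** Section 7.5 pays six survey time points and lists stool and blood-spot collection as separate items. It adds a "Bonus for Completing Above 6 Assessments". It also says that payment by check is "provided at the end of participation in the study (after the 3-month follow-up assessment", with no mention of the samples.

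**Sampling times.** The schedule in section 13.2 and the measures table in section 13.3 place both samples at pre-intervention and 3-month follow-up only.

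**Baseline safeguard.** Section 13.1, steps 2 and 4, require the baseline kit to be back before randomization.

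**App data.** Under section 13.5, HMP usage data from the two app groups "will continue to be collected until the 3-month follow-up assessment". Section 13.1, step 6, says more loosely that app data are monitored throughout the study.

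**The concern.** The third aim in section 3.1 and one of the hypotheses in section 3.2 compare HMP with both control groups on biological processes: gut microbiome, CRP, IL-6 and inflammatory gene expression. The 3-month sample is the only one taken after randomization, so it carries that comparison alone.

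If a control participant uses the full program before giving that sample, the sample no longer represents the control condition. Where the program affects biology in the same direction in controls as in the intervention group, the between-group difference shrinks. The intervention group finished its four instructed weeks about 90 days before the follow-up invite, and later use is optional. A crossed-over control could therefore have the more recent exposure.

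At baseline the plan protects the order of sampling and exposure by requiring the kit first. It has no matching rule at follow-up and gives no reason for the difference. It is also unclear whether use in the gap would be recorded, especially in the usual care group, which section 13.5 does not cover.

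**Working it through.** The plan states no figure for this gap, so there is none to reproduce. The check sets the two windows against each other.

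**Inputs**
- Day 0 is the follow-up invite (section 13.1, step 7).
- s is the day the surveys and games are finished, from 0 to 14 (2-week window, step 7).
- The kit window is 1 month, taken as 30 days (step 7).
- k is the day the kit month starts. The plan does not state it, so it is varied as an assumption.
- The full HMP is assumed to be available from day s, the earliest date that section 11.1 permits on the narrow reading of assessment.

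**Formula.** Longest possible access before sampling = (k + 30) − s, with a floor of zero.

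| Kit month starts | s = 0 | s = 7 | s = 14 |
|---|---|---|---|
| 14 days before invite (k = −14) | 16 | 9 | 2 |
| at invite (k = 0) | 30 | 23 | 16 |
| 14 days after invite (k = 14) | 44 | 37 | 30 |

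Two further cases help.
- If the follow-up month ran from survey completion, as the baseline return deadline does, then k = s and the maximum is 30 days whatever the survey date.
- If the kit month opened 30 days before the invite, the maximum would be (−30 + 30) − 0 = 0 and the problem would disappear.

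For scale, the intervention lasts 4 weeks, or 28 days.

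**How many controls could be affected.** Two-fifths plus one-fifth of 1,500 is 900 randomized to a control group. Section 4.2 expects 20 to 50% attrition. If that applies equally to the groups, 900 × 0.80 = 720 down to 900 × 0.50 = 450 controls would reach follow-up. These are the participants to whom the gap is open, not a forecast of how many would cross over.

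**Size of dilution.** If a share f of controls use the full HMP before sampling and gain a share g of its biological effect, the expected contrast becomes (1 − f × g) times its undiluted value. The documents give neither f nor g.

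**Does assessment include the kits?** Three points favour the narrow reading. Step 7 attaches the 2-week limit to the assessment and a different limit to the kits, so the two cannot share one completion date. Step 2 has the same structure at baseline, where the kit is due within a month of finishing the surveys and games. Section 7.5 itemizes the samples apart from the assessments.

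**The case against.** **The broader reading.** Step 7 carries the follow-up assessment as its title and mentions the kits in the same paragraph. Both schedule tables put the samples under the 3-month follow-up. On that view the assessment is not finished until the samples are done, and section 21.1 agrees with section 11.1. This is a fair reading, and it means the text is ambiguous rather than plainly wrong. It does not close the gap, because no sentence ties the offer to the kit and the separate windows point the other way.

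**Immediate release.** A reader might infer that controls receive the app the moment they submit the surveys. The documents do not say so. Section 11.1 says after, and in the same section it uses immediately for the release that follows randomization. The gaps above are therefore upper limits.

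**Mailing date.** The kit may already be mailed early in practice. The documents neither say so nor rule it out, so every gap in days is conditional.

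**Size.** A reader might count all 900 controls as exposed, or multiply guesses: f of 20 to 40% and g of 25 to 75% give 0.20 × 0.25 = 5% to 0.40 × 0.75 = 30% dilution. Neither step is supported. The first ignores attrition and assumes universal crossover. The second only returns its assumed inputs.

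**Access outside the offer.** Section 15 tells withdrawing participants that the app is free to use, so timing the offer may not control all access. That stands, but it is no reason to make the offer before the sample.

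**Conclusion.** The concern holds as a gap in the ordering of two events. The text allows the full HMP to reach some control participants before their only post-randomization stool and blood-spot samples, and nothing at follow-up matches the baseline kit requirement. This rests on the narrow reading of assessment, which is the more natural one but not the only one.

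The maximum gap is about 16 to 30 days if both windows open at the invite, and about 2 to 44 days if the kit month starts up to 14 days earlier or later. All of these figures assume a 30-day month and release on the day the surveys are finished. The resulting dilution cannot be estimated from the documents.

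A reader might infer that the trial's main results are at risk. They are not. Section 3.3 lists PHQ-8 as primary, and anxiety, sleep, flourishing, pattern separation and the video task as secondary. All of these are follow-up surveys or games, completed before release on either reading. What is exposed is the biological aim and hypothesis. This is an inexpensive improvement worth making, not a flaw in the primary comparison.

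**What to change.** 1. Reconcile sections 11.1, 13.1 (step 7) and 21.1 with one rule: for the active control and usual care groups, the full-HMP offer is triggered in REDCap only when the 3-month kit has been received or its 1-month window has closed.
2. State when that month starts, and mail the kit at or before the survey invite so that sampling normally comes first.
3. Record the date of HMP release and the date of each sample collection.
4. Do not rely on an analysis that drops post-release samples from the control groups only. That would select participants on behaviour after randomization in some groups and not the other, and would break the randomized comparison. If the dates are used in a sensitivity analysis, apply the same timing rule to all three groups, for example a common limit on days from invite to sample. Treat the result as supportive.

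The cost is one REDCap trigger, a mailing date and two recorded dates. Some controls would wait up to a few weeks longer for the app offer. The change helps only samples not yet collected, so it should be made before further 3-month collection.
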